- Approximately 10 mL of venous blood will be collected immediately prior to the second study vaccination for clinical safety labs (WBC, Hgb, PLT, ALT, T. Bili, and Cr), and performed by the central (clinical) laboratory. The results from this blood draw will not be available or reviewed prior to study vaccination.
- Approximately 10 mL of venous blood will be collected immediately prior to the second study vaccination for serum antibody assays.
- Approximately 10 mL of venous blood will be collected immediately prior to the second study vaccination for future research from subjects who consent to collection of serum for future use either by signing an ICF that includes collection of future use samples as a

condition of study participation or by indicating that they can opt in to sample collection for future use if the ICF allows the option to choose that option.

- Subjects will then receive a single dose of study vaccine via IM injection into the deltoid muscle of the preferred arm. The second study vaccination may be given in the same preferred arm as long as there is no interference with the reactogenicity assessment. The site of injection (right or left arm) and time of administration will be recorded on the appropriate data collection form. Subjects will be observed in the clinic for at least 20 minutes after the second study vaccination. The second study vaccination site will be examined, post-administration reactogenicity assessments will be performed, and any AE/SAEs will be recorded on the appropriate data collection form prior to discharge from the clinic.

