8.3 Reporting Procedures

Solicited injection site and systemic reactogenicity events will be documented and reported from the time of each study vaccination through 7 days after each study vaccination.

Clinical safety laboratory AEs will be documented and reported from the time of each study vaccination through approximately 7 days after each study vaccination.

Unsolicited non-serious AEs will be documented and reported from the time of each study vaccination through approximately 21 days after each study vaccination.

SAEs, MAAEs, including NOCMCs, and PIMMCs will be documented and reported from the time of the first study vaccination through approximately 12 months after the last study vaccination.

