3.2. Endpoints

3.2.1. Primary

Safety:

- Occurrence of study vaccine-related serious adverse events (SAEs) from the time of the first study vaccination through approximately 12 months after the last study vaccination.
- Occurrence of solicited injection site and systemic reactogenicity events from the time of each study vaccination through 7 days after each study vaccination.
- Occurrence of clinical safety laboratory adverse events from the time of each study vaccination through approximately 7 days after each study vaccination.

Immunogenicity:

- For HAI and Neut antibodies, percentage of subjects achieving seroconversion against the influenza 2017 H7N9 study vaccine strain (defined as either a pre-vaccination titer <1:10 and a post-vaccination titer \geq 1:40 or a pre-vaccination titer \geq 1:10 and a minimum four-fold rise in post-vaccination titer) at approximately 21 days after the second study vaccination (Study Day 43).
- For HAI and Neut antibodies, percentage of subjects achieving titer \geq 1:40 against the influenza 2017 H7N9 study vaccine strain at approximately 21 days after the second study vaccination (Study Day 43).
- Geometric Mean Titers (GMTs) of serum HAI and Neut antibodies against the influenza 2017 H7N9 vaccine strain at approximately 21 days after the second study vaccination (Study Day 43).

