4.4.5. Selection and Timing of Dose for Each Subject

Each subject is to be randomly assigned to a study group which will define the A/H7N9 vaccine dose and receipt of adjuvant for both planned study vaccinations. The first vaccination takes place on the day of randomization, and the second vaccination takes place approximately 21 days after the first vaccination (protocol defined window of 21-28 days post first vaccination).

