4.5.1. Safety Variables

Safety will be assessed by the frequency and severity of:

1. SAEs occurring from the time of the first study vaccination through approximately 12 months after the last study vaccination.
2. Solicited AEs – reactogenicity events occurring from the time of each study vaccination through 7 days after each study vaccination:
 - a) Injection site reactions including pruritus, ecchymosis, erythema, induration/swelling, pain, and tenderness.
 - b) Systemic reactions including fever, feverishness, fatigue, malaise, myalgia, arthralgia, headache, and nausea.
3. Clinical safety laboratory AEs occurring from the time of each study vaccination through approximately 7 days after each study vaccination. Parameters to be evaluated include white blood cells (WBC), hemoglobin (Hgb), platelets (PLT), alanine aminotransferase (ALT), total bilirubin (T. Bili), and creatinine (Cr).
4. Unsolicited AEs – non-serious AEs occurring from the time of each study vaccination through approximately 21 days after each study vaccination.
5. MAAEs, including NOCMCs, and PIMMCs occurring from the time of the first study vaccination through approximately 12 months after the last study vaccination.

Grading scales for injection site and systemic solicited reactions, vital signs, and clinical laboratory parameters are provided in [Table 9](#), [Table 10](#), [Table 11](#), and [Table 12](#).

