9.6. Clinical Laboratory Evaluations

Clinical safety laboratory parameters (WBC, Hgb, PLT, ALT, T. Bili, Cr) will be collected from each subject prior to each study vaccination and approximately 7 days after each study vaccination. These evaluations will be performed by the central clinical laboratory. The grading scale for clinical laboratory evaluations is presented in [Table 12](#). Clinical laboratory evaluations assessed on Day 1 prior to the first study vaccination will be considered as baseline.

The distribution of laboratory results by severity, study day, and study arm will be presented in [Table 88](#), [Table 89](#), [Table 90](#), [Table 91](#), [Table 92](#), [Table 93](#), and [Table 94](#). Descriptive statistics including mean, standard deviation, median, minimum and maximum values by study day will be summarized for each parameter and for the change from baseline for each parameter in [Table 95](#), [Table 96](#), [Table 97](#), [Table 98](#), [Table 99](#), and [Table 100](#). Box plots illustrating the change from baseline for each laboratory parameter will be presented in [Figure 25](#), [Figure 26](#), [Figure 27](#), [Figure 28](#), [Figure 29](#), and [Figure 30](#). Subject visits with

abnormal laboratory results, Grade 1 severity or higher, will be presented in [Table 101](#) and [Table 102](#) for Chemistry and Hematology parameters, respectively.

A complete listing of individual clinical laboratory results will be presented in [Listing 13](#) and [Listing 14](#) for chemistry and hematology, respectively, sorted by subject ID, parameter, and visit number.

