Malaise (General Unwell Feeling)	No interference with daily activity	Some interference with daily activity	Significant interference, prevents daily activity
Myalgia (Body Aches/Muscular Pain)*	No interference with daily activity	Some interference with daily activity	Significant interference, prevents daily activity
Arthralgia (Joint Pain)*	No interference with daily activity	Some interference with daily activity	Significant interference, prevents daily activity
Headache	No interference with daily activity	Some interference with daily activity	Significant interference, prevents daily activity
Nausea	No interference with daily activity	Some interference with daily activity	Significant interference, prevents daily activity
Quantitative Systemic Reactogenicity Grading			
Systemic (Quantitative)	Mild (Grade 1)	Moderate (Grade 2)	Severe (Grade 3)
Fever [#] - oral	38.0°C – 38.4°C 100.4°F – 101.1°F	38.5°C – 38.9°C 101.2°F – 102.0°F	>38.9°C >102.0°F
* Not at injection site.			
[#] Oral temperature assessed on Day 1 prior to the first study vaccination will be considered as baseline. A fever can be considered not related to the study product if an alternative etiology can be documented.			

Table 11: Vital Signs Adverse Event Grading Scale

For all individuals, pulse and blood pressure [#] will be graded as follows:			
Physiologic Parameter	Mild (Grade 1)	Moderate (Grade 2)	Severe (Grade 3)
Bradycardia - beats per minute	45 – 46	40 – 44	<40
Tachycardia - beats per minute	101 – 130	131 – 155	>155
Hypotension (systolic) mmHg	80 – 84	75 – 79	<75
Hypotension (diastolic) mmHg	50 – 54	45 – 49	<45
Hypertension (systolic) mmHg	151 – 155	156 – 160	>160
Hypertension (diastolic) mmHg	96 – 100	101 – 105	>105
[#] Pulse and blood pressure assessed on Day 1 prior to the first study vaccination will be considered as baseline.			

12.4.1 Individual Laboratory Measurements and Abnormal Laboratory Values**Table 12: Laboratory Adverse Event Grading Scale**

Hematology	Mild (Grade 1)	Moderate (Grade 2)	Severe (Grade 3)
WBC 10 ³ /μL (Decrease)	2.5 – 3.9	1.5 – 2.4	<1.5
WBC 10 ³ /μL (Increase)	10.6 – 15.0	15.1 – 20.0	>20.0
Hgb g/dL (Decrease) (Female)	10.1 – 11.4	8.5 – 10	<8.5
Hgb g/dL (Decrease) (Male)	11.0 – 12.4	9.5 – 10.9	<9.5
Platelets 10 ³ /μL (Decrease)	125 – 139	100 – 124	<100
Platelets 10 ³ /μL (Increase)	416 – 550	551 – 750	>750
Chemistry	Mild (Grade 1)	Moderate (Grade 2)	Severe (Grade 3)
ALT IU/L (Increase) (Female)	44 – 100	101 – 200	>200

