14.3.4 Displays of Laboratory Results

Table 88: Laboratory Results by Parameter, Maximum Severity, Study Day, and Study Arm – All Laboratory Parameters – Safety Population

Treatment Group	Study Day	N	None		Mild/ Grade 1		Moderate/ Grade 2		Severe/ Grade 3		Missing	
			n	%	n	%	n	%	n	%	n	%
Study Arm 1 3.75 mcg A/H7N9 + MF59	Baseline	x	x	xx	x	xx	x	xx	x	xx	x	xx
	Day 8											
	Day 22											
	Day 29											
	Max Severity Post Baseline											
[Repeat for all Study Arms]												

Note: N = Number of subjects in the Safety population.
The “Max Post Baseline” rows indicate the maximum severity experienced by each subject at any time point post baseline, including unscheduled assessments.

Tables with similar format:

Table 89: Laboratory Results by Parameter, Maximum Severity, Study Day, and Study arm – Hemoglobin – Safety Population

Table 90: Laboratory Results by Parameter, Maximum Severity, Study Day, and Study arm – Alanine aminotransferase (ALT) – Safety Population

Table 91: Laboratory Results by Parameter, Maximum Severity, Study Day, and Study arm – Total Bilirubin – Safety Population

Table 92: Laboratory Results by Parameter, Maximum Severity, Study Day, and Study arm – Creatinine – Safety Population

Table 93: Laboratory Results by Parameter, Maximum Severity, Study Day, and Study Arm – White Blood Cells – Safety Population

Treatment Group	Study Day	N	None		Mild/ Grade 1 (Low)		Mild/ Grade 1 (High)		Moderate/ Grade 2 (Low)		Moderate/ Grade 2 (High)		Severe/ Grade 3 (Low)		Severe/ Grade 3 (High)		Missing	
			n	%	n	%	n	%	n	%	n	%	n	%	n	%	n	%
Study Arm 1 3.75 mcg A/H7N9 + MF59	Baseline	x	x	xx	x	xx	x	xx	x	xx	x	xx	x	xx	x	xx	x	xx
	Day 8																	
	Day 22																	
	Day 29																	
	Max Severity Post Baseline																	
[Repeat for all Study Arms]																		

Note: N = Number of subjects in the Safety population.
The “Max Post Baseline” rows indicate the maximum severity experienced by each subject at any time point post baseline, including unscheduled assessments.

Table with similar format:

Table 94: Laboratory Results by Parameter, Maximum Severity, Study Day, and Study Arm – Platelets – Safety Population

Table 95: Laboratory Summary Statistics of Value and Change from Baseline by Parameter, Study Day, and Study Arm – White Blood Cells - Safety Population

Treatment Group	Study Day	Value					Change from Baseline				
		N	Mean	Standard Deviation	Median	Min, Max	N	Mean	Standard Deviation	Median	Min, Max

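### No planned by-arm table counts subjects with a laboratory adverse event in the primary endpoint's 7-day window, and the one cross-visit row covers more than that window

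*SAP*

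**What the plan says.** SAP 3.2.1 lists as a primary safety endpoint "Occurrence of clinical safety laboratory adverse events from the time of each study vaccination through approximately 7 days after each study vaccination". SAP 4.5.1 repeats the window and names the six parameters. Protocol 8.3 limits reporting to the same period: "Clinical safety laboratory AEs will be documented and reported from the time of each study vaccination through approximately 7 days after each study vaccination". The grades are absolute cut-offs, in Protocol 8.5 and in SAP Table 12 ("Laboratory Adverse Event Grading Scale").

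On baseline, SAP 9.6 says only this: "Clinical laboratory evaluations assessed on Day 1 prior to the first study vaccination will be considered as baseline". It then plans:

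- Tables 88-94: absolute grade by visit and arm, with rows for Baseline, Day 8, Day 22, Day 29 and Max Severity Post Baseline. The footnote says that the last "rows indicate the maximum severity experienced by each subject at any time point post baseline, including unscheduled assessments".
- Tables 95-100 and box plots: values and change from baseline on the continuous scale.
- Tables 101-102: subject listings of Grade 1 or higher results.

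Elsewhere, Table 64 includes laboratory events, but only above a 5% threshold and with no window or Day 1 rule. Topline Table 63 has no laboratory row.

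**The concern.** The other two primary safety endpoints have by-arm subject counts: solicited events in Tables 65-67 with exact intervals, and related serious events as a row of Table 63. The laboratory endpoint has none. A reader who wants one figure per arm would turn to the maximum row, which covers a longer period than the endpoint and takes no account of Day 1. Protocol 10.1 says that the trial is meant to estimate responses and uncover safety issues, not to test a formal hypothesis. What is at stake is therefore the reported safety rate. If the counting rule is left open, it would be chosen after the data are seen, although Protocol 10.5 calls for the SAP to be final before unblinding.

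**Working it through.** **1. Which draws fall where.** The Day 22 sample is taken "immediately prior to the second study vaccination for clinical safety labs", and dose 2 has a "protocol defined window of 21-28 days post first vaccination".

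| Draw | In the endpoint window? | In the maximum row? |
|---|---|---|
| Day 1, before dose 1 | No (baseline) | No |
| Day 8, about 7 days after dose 1 | Yes | Yes |
| Day 22, 21-28 days after dose 1 and before dose 2 | No | Yes |
| Day 29, about 7 days after dose 2 | Yes | Yes |
| Unscheduled, any time (Protocol 6.5) | Only if soon after a dose | Yes |

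**2. Direction of the mismatch.** Let M be subjects graded at any post-baseline draw, A those graded in the window, and W those whose in-window grade is above Day 1. Everyone in W is in A, and everyone in A is in M. So W ≤ A ≤ M, and this needs no assumed rates.

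**3. What the visit rows can supply.** Suppose 8 of 106 subjects are graded on each of Day 1, Day 8 and Day 29.
- A lies between 8 (the same 8 subjects) and 8 + 8 = 16 (different subjects).
- W lies between 0 (the same 8 throughout) and 16 (different subjects each time).

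The rows fix neither count.

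**4. The Day 1 grade.** Protocol 3.1 says that Day 1 laboratory results do not screen for eligibility, so graded Day 1 values can enter the trial. SAP 4.1 says that hematology and biochemistry must be in an acceptable range at entry. The two passages must be reconciled. Protocol 8.1.1 records a pre-existing medical condition as an unsolicited event only if it increases in severity or frequency. It is not worded for laboratory grades and is not carried into SAP 9.6.

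**5. Illustrative size.** The documents give neither the prevalence of graded results nor how long they persist, so these inputs are assumed:
- eight graded directions from SAP Table 12 (WBC and platelets low and high; hemoglobin low; ALT, bilirubin and creatinine high);
- no vaccine effect, six independent normally distributed parameters, and no unscheduled draws;
- tail probability p per direction per draw, and within-subject correlation r between draws at Days 1, 8, 22 and 29.

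The share graded at one draw is 1 − (1−2p)²(1−p)⁴, which is 7.7% at p = 1% and 18.4% at p = 2.5%. Simulating 1,000,000 subjects per setting gives (simulation error about 0.1 percentage point):

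| p | r | Maximum row (M) | Any grade, Day 8 or 29 (A) | Newly graded vs Day 1 (W) | M/A | M/W |
|---|---|---|---|---|---|---|
| 1% | 0.5 | 19.4% | 14.2% | 12.5% | 1.37 | 1.55 |
| 1% | 0.8 | 15.7% | 12.3% | 8.5% | 1.27 | 1.86 |
| 2.5% | 0.5 | 41.0% | 31.4% | 26.7% | 1.31 | 1.53 |
| 2.5% | 0.8 | 33.5% | 27.5% | 17.8% | 1.22 | 1.88 |

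Per 106 subjects, the maximum row exceeds A by about 3.5-10 and W by about 7-17. Between 38% and 77% of the excess over W is seen only at Day 22; the rest is carried over from Day 1. With wider inputs (p from 0.5% to 5%, r from 0.3 to 0.9), M/W runs from 1.4 to 2.3.

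**The case against.** The strongest reply is that neither document defines the endpoint as worsening from Day 1. The grades are absolute. If any grade in the window is the event, the Day 8 and Day 29 rows already give by-arm counts at the right visits, beside a Baseline row, and all that is missing is one combined row. The SAP never calls the maximum row the endpoint analysis. The listings would let anyone derive either count. Randomization should make the overstatement about equal across arms.

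Most of this stands. It lowers the illustrative excess to 1.2-1.4 times and makes 1.5-1.9 times conditional on a worsening definition. It does not remove the gap: even on the absolute reading, no by-arm per-subject count for the window is planned, and the SAP does not say which reading applies. The listings preserve the data but do not set the counting rule in advance.

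**Conclusion.** Followed as written, the plan yields no by-arm count of subjects for this primary safety endpoint, and its nearest single figure can only equal or exceed that count. This rests on the table layout alone. The ratios of 1.2-1.4 (any grade in the window) and 1.5-1.9 (worsened in the window) rest on assumed prevalence, correlation and independence, and show only what is plausible. If SAP 4.1's entry requirement were the operative one, carry-over from Day 1 would be smaller, but the Day 22 and unscheduled draws would still be included.

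A reader might infer that the endpoint means worsening and that the plan misreports it by up to 1.9 times. The documents do not support that, because they leave the role of the Day 1 grade open. Nor do they support a claim of biased arm comparisons: no planned between-arm test uses these rows. Severity is minor to moderate.

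**What to change.** In SAP 9.6, define a laboratory adverse event, for each parameter and direction, as a grade higher than Day 1 at the Day 8 or Day 29 visit, or at an unscheduled or early-termination draw in the post-vaccination window. State the window's upper bound consistently with SAP 6.3.3, which accepts Visits 3 and 6 up to 10 days after vaccination. Then:

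- report subjects with at least one such event by arm, with exact 95% confidence intervals, and add that row to Table 63;
- use the same definition in Table 64;
- add a shift table from the Day 1 grade to the worst in-window grade, by arm and parameter;
- also show the count with any absolute grade in the window, so both readings are visible;
- keep Tables 88-94, including the Day 22 row, as supportive;
- reconcile SAP 4.1 with Protocol 3.1 on laboratory values at entry.

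The cost is a small amount of programming for the derived flags, the added rows and one shift table. No new data are needed. The headline count will be no larger than the maximum row, and probably smaller.

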14.3.4.5 Clinical Laboratory Reference Ranges

(Placeholder for the CSR)

14.3.5 Abnormal Laboratory Value Listings (by Subject)

Table 101: Listing of Abnormal Laboratory Results - Chemistry

Subject ID	Study Arm	Sex	Age (years)	Planned Time Point	Actual Study Day	Laboratory Parameter (Units)	Result (Severity)	Relationship to Treatment	If Not Related, Alternate Etiology	Action Taken with Study Treatment	Subject Discontinued Due to Result?

Table 102: Listing of Abnormal Laboratory Results - Hematology

Subject ID	Study Arm	Sex	Age (years)	Planned Time Point	Actual Study Day	Laboratory Parameter (Units)	Result (Severity)	Relationship to Treatment	If Not Related, Alternate Etiology	Action Taken with Study Treatment	Subject Discontinued Due to Result?

14.3.6 Displays of Vital Signs

Table 103: Vital Signs by Assessment, Maximum Severity, Study Day, and Study Arm – Any Assessment - Safety Population

Treatment Group	Study Day	N	None		Mild		Moderate		Severe		Missing	
			n	%	n	%	n	%	n	%	n	%
Study Arm 1 3.75 mcg A/H7N9 + MF59	Baseline	x	x	xx	x	xx	x	xx	x	xx	x	xx
	Day 22											
	Max Severity Post Baseline											
[Repeat for all Study Arms]												
Note: N = Number of subjects in the Safety population.												
The “Max Post Baseline” rows indicate the maximum severity experienced by each subject at any time point post baseline, including unscheduled assessments.												

Table with similar format:

Table 104: Vital Signs by Assessment, Maximum Severity, Study Day, and Study Arm – Oral Temperature - Safety Population

Table 105: Vital Signs by Assessment, Maximum Severity, Study Day, and Study Arm – Systolic Blood Pressure - Safety Population

Treatment Group	Study Day	N	None		Mild (Low)		Mild (High)		Moderate (Low)		Moderate (High)		Severe (Low)		Severe (High)		Missing	
			n	%	n	%	n	%	n	%	n	%	n	%	n	%	n	%
Study Arm 1 3.75 mcg A/H7N9 + MF59	Baseline	x	x	xx	x	xx	x	xx	x	xx	x	xx	x	xx	x	xx	x	xx
	Day 22																	
	Max Severity Post Baseline																	
[Repeat for all Study Arms]																		
Note: N = Number of subjects in the Safety population.																		
The “Max Post Baseline” rows indicate the maximum severity experienced by each subject at any time point post baseline, including unscheduled assessments.																		

Tables with similar format:

Table 106: Vital Signs by Assessment, Maximum Severity, Study Day, and Study Arm – Diastolic Blood Pressure - Analysis Population

Table 107: Vital Signs by Assessment, Maximum Severity, Study Day, and Study Arm – Pulse - Safety Population

14.4 Summary of Concomitant Medications

Table 108: Number and Percentage of Subjects with Prior and Concurrent Medications by WHO Drug Classification and Study Arm- Safety Population

WHO Drug Code Level 1, Anatomic Group	WHO Drug Code Level 2, Therapeutic Subgroup	Study Arm 1 3.75 mcg A/H7N9 + MF59 (N=X)		Study Arm 2 7.5 mcg A/H7N9 + MF59 (N=X)		Study Arm 3 15 mcg A/H7N9 + MF59 (N=X)		Study Arm 4 15 mcg A/H7N9 (N=X)	
		n	%	n	%	n	%	n	%
Any Level 1 Codes	Any Level 2 Codes	x	xx	x	xx	x	xx	x	xx
[ATC Level 1 - 1]	Any [ATC 1 - 1]								
	[ATC 2 - 1]								
	[ATC 2 - 2]								
	[ATC 2 - 3]								
[ATC Level 1 - 2]	[ATC 2 - 1]								
	[ATC 2 - 2]								
	[ATC 2 - 3]								

N= Number of subjects in the Safety population; n=Number of subjects reporting taking at least one medication in the specific WHO Drug Class.

[figure not shown]

10.1 Disposition of Subjects Figures

[figure not shown]
Figure 1: CONSORT Flow Diagram

14.2.2 Immunogenicity Figures

Figure 2: Reverse Cumulative Distribution of Hemagglutination Inhibition Antibody against A/Hong Kong/125/2017 (H7N9) by Study Day, and Study Arm - Modified Intent to Treat Population

[Implementation Note: A generic sample figure is shown below. The RCD curves should be presented in a single figure with separate panels for each study day (Baseline, Day 8, Day 22, Day 29, Day 43, Day 202). Figures generated for preliminary report will include data from all available visits at the time of report generation. Visit labels should be included in the panel headers. Within each panel individual curves should be used for each study arm (four curves).]

Figures with similar format:

Figure 3: Reverse Cumulative Distribution of Hemagglutination Inhibition Antibody against A/Hong Kong/125/2017 (H7N9) by Study Day, and Study Arm - Per-Protocol Population

[figure not shown]
Figure 4: Reverse Cumulative Distribution of Neutralizing Antibody Against A/Hong Kong/125/2017 (H7N9) by Study Day, and Study Arm - Modified Intent-to-Treat Population

Figure 5: Reverse Cumulative Distribution of Neutralizing Antibody against A/Hong Kong/125/2017 (H7N9) by Study Day, and Study Arm - Per-Protocol Population

Figure 6: Geometric Mean Titers of Hemagglutination Inhibition Antibody Against A/Hong Kong/125/2017 (H7N9) by Study Day, and Study Arm - Modified Intent-to-Treat Population

[Implementation Note: A generic sample figure is shown below. Planned Study Day is plotted along the x-axis, with visit labels as tick labels. Titer is plotted on the y-axis on the log-10 scale. GMT should be plotted at each visit with upper and lower error bars for the 95% CI for each treatment group with different marker shapes/colors for each study arm. Each study arm should have a separate color and marker shape.]

Note: this figure will be generated for the preliminary report including data through Day 43, then re-generated for the final CSR to include all data through Day 202.

Figures with similar format:

Figure 7: Geometric Mean Titers of Hemagglutination Inhibition Antibody against A/Hong Kong/125/2017 (H7N9) by Study Day and Study Arm - Per-Protocol Population

Figure 8: Geometric Mean Titers of Neutralizing Antibody against A/Hong Kong/125/2017 (H7N9) Study Day and Study Arm - Modified Intent-to-Treat Population

Figure 9: Geometric Mean Titers of Neutralizing Antibody against A/Hong Kong/125/2017 (H7N9) by Study Day and Study Arm - Per-Protocol Population

Figure 10: Correlation of Hemagglutination Inhibition Antibody and Neutralizing Antibody Against A/Hong Kong/125/2017 (H7N9) by Study Day and Study Arm - Modified Intent-to-Treat Population

[Implementation Note: A generic sample figure is shown below. The scatter plots should be presented in a single figure with separate panels for each visit (Baseline, D8, D22, D29, D43, D202. Visit labels should be included in the panel header. Within each panel distinct marker types and colors should be used to indicate the study arms, with treatment group labels included in a legend.). Each study arm should have a unique color and marker shape. The spearman correlation should be calculated over all subjects and annotated within each panel as “Spearman Correlation ($r=0.xx$, $p=0.xx$)”.]

[figure not shown]

Figure with Similar format:

Figure 11: Correlation of Hemagglutination Inhibition Antibody and Neutralizing Antibody Against A/Hong Kong/125/2017 (H7N9) by Study Day and Study Arm - Per-Protocol Population

Figure 12: Reverse Cumulative Distribution of Hemagglutination Inhibition Antibody against A/Shanghai/2/2013 (H7N9) by Study Day and Study Arm - Per-Protocol Population

[Implementation Note: A generic sample figure is shown below. The RCD curves should be presented in a single figure with separate panels for each study day (Baseline[Day1], Day 8, Day 22, Day 29, Day 43, Day 202. Visit labels should be included in the panel headers. Within each panel individual curves should be used for each study arm (four curves). Each study arm should have a separate color.]

[Implementation Note: repeat for all heterologous strains]

[figure not shown]

Figure with Similar Format:

Figure 13: Reverse Cumulative Distribution of Hemagglutination Inhibition Antibody against A/Guangdong/17SF003/2016 (H7N9) by Study Day and Study Arm - Per-Protocol Population

[figure not shown]
Figure 14: Reverse Cumulative Distribution of Neutralizing Antibody against A/Shanghai/2/2013 (H7N9) by Study Day and Study Arm - Per-Protocol Population

Figure 15: Reverse Cumulative Distribution of Neutralizing Antibody against A/Guangdong/17SF003/2016 (H7N9) by Study Day and Study Arm - Per-Protocol Population

Figure 16: Geometric Mean Titers of Hemagglutination Inhibition Antibody against A/Shanghai/2/2013 (H7N9) by Study Day and Study Arm - Per-Protocol Population

[Implementation Note: A generic sample figure is shown below. Planned Study Day is plotted along the x-axis, with visit labels as tick labels. Titer is plotted on the y-axis on the log-10 scale. GMT should be plotted at each visit with upper and lower error bars for the 95% CI for each treatment group with different marker shapes/colors for each study arm.]

[Implementation Note: repeat for all heterologous strains]

Figures with similar format:

Figure 17: Geometric Mean Titers of Neutralizing Antibody against A/Guangdong/17SF003/2016 (H7N9) by Study Day and Study Arm - Per-Protocol Population

[figure not shown]
Figure 18: Geometric Mean Titers of Hemagglutination Inhibition Antibody against A/Shanghai/2/2013 (H7N9) by Study Day and Study Arm - Per-Protocol Population

Figure 19: Geometric Mean Titers of Neutralizing Antibody against A/Guangdong/17SF003/2016 (H7N9) by Study Day and Study Arm - Per-Protocol Population

Figure 20: Correlation of Hemagglutination Inhibition Antibody and Neutralizing Antibody Against A/Shanghai/2/2013 (H7N9) by Study Day and Study Arm - Per-Protocol Population

[Implementation Note: A generic sample figure is shown below. The scatter plots should be presented in a single figure with separate panels for each visit (Baseline, D8, D22, D29, D43, D202. Visit labels should be included in the panel header. Within each panel distinct marker types and colors should be used to indicate the study arms, with treatment group labels included in a legend. Each study arm should have a unique color and marker shape. The spearman correlation should be calculated over all subjects and annotated within each panel as “Spearman Correlation ($r=0.xx$, $p=0.xx$)”.]

[Implementation Note: repeat for all heterologous strains]

Figures with similar format (may repeat as needed for additional strains):

Figure 21: Correlation of Hemagglutination Inhibition Antibody and Neutralizing Antibody Against A/Guangdong/17SF003/2016 (H7N9) by Study Day and Study Arm - Per-Protocol Population

Figure 22: Correlation of Hemagglutination Inhibition Antibody Against 2017 A/H7N9 and A/Shanghai/2/2013 (H7N9) by Study Day and Study Arm - Per-Protocol Population

Figure 23: Correlation of Hemagglutination Inhibition Antibody Against 2017 A/H7N9 and A/Guangdong/17SF003/2016 (H7N9) by Study Day and Study Arm - Per-Protocol Population

Figure 24: Correlation of Neutralizing Antibody Against 2017 A/H7N9 and A/Shanghai/2/2013 (H7N9) by Study Day and Study Arm - Per-Protocol Population

Figure 25: Correlation of Neutralizing Antibody Against 2017 A/H7N9 and A/Guangdong/17SF003/2016 (H7N9) by Study Day and Study Arm - Per-Protocol Population

